### 5.5: Diet registration

Diet registration will be performed by the participants during the screening period and every 16 weeks. The daily intake of all food will be recorded daily in four consecutive days after inclusion in the screening period and after every 16-week visits. A pre-evaluated questionnaire based “diet.no” will be used and recorded on an electronical diet APP by the participants. The diet registration will be supervised by a qualified monitor.

### 5.6: Adverse Events (AE)

#### 5.6.1: Common Terminology Criteria for Adverse Events version 4.0 (CTCAE)

The CTCAE is divided in 26 System Organ Class (SOC) in accordance with the MedDRA hierarch. Within each SOC, AE are listed and accompanied by descriptions of severity or grade:

- Blood and lymphatic system disorders (11 Items)
- Cardiac disorders (36 Items)
- Congenital, familial, and genetic disorders (1 Items)
- Ear and labyrinth disorders (9 Items)
- Endocrine disorders (11 Items)
- Eye disorders (25 Items)
- Gastrointestinal disorders (117 Items)
- General disorders and administration site conditions (24 Items)
- Hepatobiliary disorder (16 Items)
- Immune system disorders (6 Items)
- Infections and infestations (76 Items)
- Injury, poisoning and procedural complications (78 Items)
- Investigations (38 Items)
- Metabolism and nutrition disorders (24 Items)
- Musculoskeletal and connective disorders (41 Items)
- Neoplasms benign, malignant and unspecified incl. cysts and polyps (5 Items)
- Nervous system disorders (63 Items)
- Pregnancy, puerperium and perinatal conditions (5 Items)

- Psychiatric disorders (20 Items)
- Renal and urinary disorders (20 Items)
- Reproductive system and breast disorders (51 Items)
- Respiratory, thoracic and mediastinal disorders (59 Items)
- Skin and subcutaneous tissue disorders (34 Items)
- Social circumstances (2 Items)
- Surgical and medical procedures (1 Item)
- Vascular disorders (17 Items)

### 5.6.2: Grading and classification

Grade refers to the severity of the AE. The CTCAE displays Grade 1 through 5 with unique clinical descriptions of severity for each AE based on this general guideline:

Grade 0 =	None
Grade 1 =	Mild: asymptomatic or mild symptoms; clinical or diagnostic. Observations only; intervention not indicated.
Grade 2 =	moderate: minimal, local, or non-invasive intervention indicated; Limiting age-appropriate instrumental Activity of Daily Living (ADL)
Grade 3 =	severe or medically significant but not immediately life-threatening; Hospitalization or prolongation of hospitalization indicated; disabling; Limiting self-care ADL
Grade 4 =	Life-threatening consequences; urgent intervention indicated
Grade 5 =	Death related to AE.

Relation to trial medication as: Definitely, Probably, Possibly or Unrelated

Action taken as: None, Interruption, Modified or Discontinued

AE treatment as: None, Continue Medication, Procedure or Hospitalization.

Outcome at last visit as: Resolved, Ongoing or Fatal.

Definitions of relationship to study treatment are as follows:

Unrelated:	bears no relation to timing of medication, like symptoms or signs expected in the disease process, does not recur on re-challenge.
Possibly:	bears relation to timing of medication, like symptoms or signs expected in the disease process, does not recur on re-challenge.
Probably:	bears clear relation to timing of medication, distinct from symptoms or signs expected in the disease process, does not recur on re-challenge.
Definitely:	bears clear relation to timing of medication, distinct from symptoms or signs expected in the disease process, recurs on re-challenge.

### 5.6.3: Reporting adverse events.

An adverse event (AE) is any untoward symptom or sign befalling a patient in a clinical trial regardless of its relationship to the study medications. All AEs must be described in detail and their severity and putative relationship to the study medication noted.

AEs may be considered serious. The definition of this is as follows:

- Death
- Life threatening
- Leads to or prolongs hospitalization
- Results in persistent of significant disability
- Any new important medical information.

### 5.7 Patient factors, Vital signs, and Physical examination.

The patient factors to be recorded in the study will be age in years from birth to the screening visit, height in cm and body weight in kg. Previous medical history, duration of any disease in months from the final diagnosis to the screening visit, previous and on-going treatment of the disease will be observed. During each physical examination, body weight, concomitant disease and treatment will be recorded. Additionally, vital signs defined as Systolic and Diastolic blood pressure in mmHg and Heart rate in beats/min will be recorded in sitting position after five-minute rest. The patients will daily recording the intake of study treatment and physical activity on a compliance & activity form.

## VI: Study procedure

### 6.1: Definitions

Important definitions are:

Osteocalcin Ratio ( $R_o$ ): cOC / uOC.

### 6.2 Clinical procedure

#### 6.2.1: Screening phase

The recruited patients fulfilling the inclusion and avoided the exclusion criteria will be registered and asked to participate in the study. The patients who are willing to sign the informed consent form will be enrolled in the study. The first part of the study is a screening phase of one week duration. The participants will undergo a clinical investigation and an appointment for the starting visit in the study one week later. In the meantime, a dietary record, activity record and the first DXA for measurement of BMD will be performed. The dietary measurements will be supervised by the monitor. All the participants will be instructed not to change their usual intake of food during the study but change their usual consumed cheese with the study cheese. During this screening period an initial clinical examination will be performed. At this baseline visit, all demographic data, social factors, history of disease and vital signs will be recorded. Blood samples will be collected for measurements of Osteocalcin, vitamin K2 and DHNA; Hematological and biochemical variables including HbA1C and Lipids, together with the BTMs and Interleukins. At the baseline visit all the patients will receive 20 $\mu$ g vitamin D and 1000 mg Ca for 4 weeks. Additionally, half of the patients will randomly be allocated to daily OED of Jarlsberg cheese and receives cheese for the next 4 weeks. All the patients will receive a registration form for daily intake of Jarlsberg cheese and vitamin D + Ca. The trial cheese can be consumed with other food at breakfast, lunch, or other meals during the day. The cheese may also be consumed heated/melted. New supply of vitamin D + Ca and cheese will be handed over to the patients by the one responsible person for the Meddoc team together with a new registration form.

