## 1.8: Study procedure

### 1.8.1 Screening and baseline

Participants, who fulfil the inclusion criteria, do not meet any of the exclusion criteria and willing to give informed consent to participate will be included in a screening period of one week. During this screening week, all the possible participants will receive 40 $\mu$ g vitamin D and 500 mg Ca tablets per day but asked not to eat Jarlsberg cheese.

DXA with BMD measurements will be taken at the start of the screening week. Patients with a BMD T-score  $\leq -1.0$  will be included in the study starting with baseline measurements (Day 0). All demographic data, social factors, history of disease and vital signs will be recorded at baseline. The participating patients will be given a Diet-App on the web or mobile phone for registration of the daily food intake during four first consecutively days after baseline. Blood samples for measurements of Osteocalcin, CTX-1, PINP, BALP, PTH and vitamin K will be taken fastening in the morning. Additionally, blood samples for measuring biochemical variables, HbA1C, Lipids, Interleukins and Cytokines, will be recorded. The Common Terminology Criteria for Adverse Events (CTCAE) version 4.0 used for measuring and classifying the tolerability and toxicity will be recorded as well. The patients will be given compliance & activity form and asked to write down the daily intake of treatment medicine, Jarlsberg cheese and hours of physical activities.

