## IV: Design and randomization

### 4.1: Study design

The study is performed as an open randomized semi crossover design with two strata. Sex is used as a stratification factor (Figure 1). The two strata are chosen because of different OED of cheese for women and men. Within each stratum the participants will be allocated either to vitamin D + Calcium alone (Control) or with daily OED of Jarlsberg cheese (Jarlsberg). The two groups will run parallelly in 16 weeks and BMD recorded by DXA. Patient with T-score < -2.5 classifies as Osteoporotic patients will be withdrawn from the study. At week 16, the patients in the control-group will be switched to additional daily OED of Jarlsberg cheese for 32 weeks. The patients randomised to Jarlsberg will continue with the same treatment for additionally 16 weeks.

[figure not shown]

Figure 2: Study design with time schedule and variables to be recorded. Measurements given in red (x) is related only to the patients initially randomised to only vitamin D + Ca (control).

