## VII. Consideration

### 8.1: Consideration of steering committee

The study will be carried out according to the Helsinki declaration with latest amendments, Good Clinical Practice (GCP) and International Ethical Guidelines for Health-related Research Involving Humans (CIOMS guidelines). The participants are risk patient for Osteoporosis and will only be included in this clinical trial after approval of the trial by the regional Ethical Committee (REK) and the patients have received oral and written information and signed informed consent.

The product to be used in this trial is Jarlsberg cheese commercially available in Norway. To the best of our knowledge, no AE is reported except from person with intolerance of milk and milk product. It is known that vitamin K2 passing a certain daily dose may increase and strengthen the bone density and may therefore have a prophylactic effect on bone fracture. Jarlsberg cheese is shown to be one of the Norwegian produced cheeses with the highest level of vitamin K2.

In a previously conducted dose-response study on healthy fertile women we found the optimal efficacy dose (OED) to increase the osteocalcin levels. Our hypothesis is that this effect is caused by the fermentation of lactic acid to propionic acid by the *Propionibacterium freudenreichii* in the Jarlsberg Cheese, producing MK 9-4H K2 vitamer and DHNA. The first aim of this study is to compare the effects with the commonly used prophylactic treatment of vitamin D + calcium to verify the hypothesis. Our second aim is to study the development of BTM and BMD by the OED of Jarlsberg Cheese and to verify if the cheese could be recommended as prophylactical treatment to osteoporosis.

All participants invited to this clinical trial are entitled to make their decision based on the fullest amount of information available at that time. To make the choice, they will be given a written document expressed in a clear concise language of their native tongue to consider. The document will tell potential participants about the aim of the study. Additionally, that blood sampling will be performed between five and seven times in connection with clinical examinations during the two study parts.

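### The no-Jarlsberg request lapses at baseline, so controls who habitually eat the cheese may resume it during the only randomised comparison; the clearest effect is on osteocalcin and bone markers

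*Protocol*

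**What the plan says.** - **Screening week.** Synopsis 1.8.1 gives all potential participants supplements for one week, "but asked not to eat Jarlsberg cheese". No later section shown repeats this request.
- **During the study.** Section 6.2.1 states "All the participants will be instructed not to change their usual intake of food during the study", and the same sentence continues "but change their usual consumed cheese with the study cheese". It makes no distinction between arms.
- **Who holds study cheese.** At baseline, "half of the patients will randomly be allocated to daily OED of Jarlsberg cheese and receives cheese for the next 4 weeks" (6.2.1). The other half wait: "At week 16, the patients in the control-group will be switched to additional daily OED of Jarlsberg cheese for 32 weeks" (4.1).
- **The randomised period.** "The two groups will run parallelly in 16 weeks and BMD recorded by DXA" (4.1). After that, every remaining patient is on Jarlsberg.
- **Access outside the trial.** "The product to be used in this trial is Jarlsberg cheese commercially available in Norway" (8.1). The exclusion criteria in 3.2.2 do not mention habitual Jarlsberg use.
- **Recording.** "All the patients will receive a registration form for daily intake of Jarlsberg cheese and vitamin D + Ca" (6.2.1). MK-9(4H) is measured at baseline and every 16 weeks (5.3 and the flow chart).

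**The concern.** The sentence in 6.2.1 has two halves. The swap half gives controls nothing to act on before week 16, because they have no study cheese. What is left for them is to eat as usual, and for a habitual Jarlsberg eater that includes Jarlsberg. The screening-week request shows that the authors regard background Jarlsberg as something to control, yet it ends just as the comparison begins.

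The other reading is that controls give up their usual cheese with nothing in its place. That contradicts the first half of the sentence and makes a different comparator. Either way the control diet for weeks 0 to 16 is not defined. Because controls cross to Jarlsberg at week 16, a contrast diluted before then cannot be recovered later.

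**Working it through.** **1. The instructions by period, for a control**

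| Period | Jarlsberg instruction | Study cheese held |
|---|---|---|
| Screening week | Avoid (1.8.1) | None |
| Day 0 to week 16 | Usual food; swap usual cheese for study cheese (6.2.1) | None |
| Week 16 onward | Take the allocated daily amount (4.1, 6.2.2) | Yes |

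The middle row is the gap. Section 4.1 defines control as vitamin D and calcium alone, but that describes the allocation and tells the patient nothing about cheese bought outside the trial.

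**2. Osteocalcin and bone markers**

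Under 1.8.1 the baseline blood sample is drawn on day 0, after a week off Jarlsberg. The next samples are at weeks 4 and 16. Section 2.1 reports that PINP, total and carboxylated osteocalcin and the osteocalcin ratio rose within 6 weeks on 57 g/day. It also reports that the comparison group's markers rose after switching to Jarlsberg. If markers follow current intake on that time scale, a control who resumes Jarlsberg on day 0 moves in the same direction as the treated arm. In such a patient the comparison is allocated dose against habitual dose, not dose against none, so the arm difference shrinks.

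**3. BMD**

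The main variable is change in BMD, and comparisons are adjusted for the baseline value (1.7, 11.2). In 1.8.1 the first DXA is at the start of the screening week; 6.2.1 places it between the clinical investigation and the starting visit. At most about a week of abstention precedes it, so a habitual eater's baseline BMD already reflects usual intake. Resuming that intake gives no reason to expect a new gain. Dilution could still come from controls who eat more Jarlsberg than before, or from habitual eaters in the Jarlsberg arm who have less to gain.

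**4. Reproducing the planned size**

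Inputs: difference 1 SD = 0.09 g/cm², 5% level, 1:1 allocation, 24 completers per arm (1.9, 11.3). A two-sided test is assumed, since sidedness is not stated.

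n per arm = 2(z₀.₉₇₅ + z₀.₉₀)² / d² = 2(1.960 + 1.282)² / 1² = 21.02, rounded up to 22 (23 with the t distribution). The stated 24 is within two patients of this. At the 95% power given in 11.3 the same formula gives 26 (27 with t). With 24 per arm, t-test power is 92.4%.

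**5. Illustrative worst case for BMD**

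Let f be the share of controls eating a trial-like amount and q the share of the planned effect lost in each. The contrast is d = 1 − f·q. The protocol gives neither quantity, so both are assumed. With q = 1:

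| f | d (SD) | g/cm² (d × 0.09) | Power, 24 per arm | Completers per arm for 90% |
|---|---|---|---|---|
| 0% | 1.0 | 0.090 | 92.4% | 23 |
| 10% | 0.9 | 0.081 | 86.3% | 27 |
| 20% | 0.8 | 0.072 | 77.4% | 34 |
| 30% | 0.7 | 0.063 | 66.1% | 44 |

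With q = 0.5, f = 20% gives d = 0.9 and 86.3%; f = 30% gives d = 0.85 and 82.2%. By step 3, q = 1 does not describe a habitual eater who merely resumes usual intake. The table bounds the problem; it does not estimate it.

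**6. What would reveal control-arm intake**

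- The daily form covers Jarlsberg for all patients, so it can.
- MK-9(4H) at baseline and week 16 can help, although section 2.3 notes that some other cheeses contain it too.
- The diet record tied to week 16 cannot. It covers the four days after the visit (6.2.2), when controls have already been handed Jarlsberg.
- The baseline diet record is in the first four days after baseline in 1.8.1 but in the screening period in 5.5 and 6.2.1. Only the former could show resumption.

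**The case against.** The strongest objection is that the mechanism does not fit habitual eaters on the main endpoint. Their baseline BMD already includes their usual intake, so treating each as gaining a full SD is wrong. This stands. A reader might infer from the power table that the BMD comparison is expected to lose 6 to 26 percentage points of power. The documents do not support that: they give no share of eaters, and the table assumes a full new gain in each.

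Second, detection is already planned through the daily form and MK-9(4H). This also stands, and a reader should not infer that contamination would go unseen. But recording does not prevent intake, and adjusting for intake after randomisation does not restore the randomised contrast.

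Third, the aim could be read as adding the cheese to an unchanged diet, in which case background Jarlsberg is part of the comparison. That is a legitimate question, but the text does not consistently pose it: the swap clause replaces usual cheese instead of adding to it, and the screening-week request would serve little purpose.

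Fourth, abstention is not neutral. A habitual eater in the control arm would stop cheese after a baseline DXA taken on usual intake, and nothing in the protocol shows that stopping lowers BMD. This stands as a cost of the fix.

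Finally, arm-specific diet advice may be in the patient information (appendix 14.5), which is not available here. The body of the protocol would still need to agree with it.

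**Conclusion.** The concern holds in a limited form. The protocol's only request to avoid Jarlsberg covers the screening week, and the study-long instruction lets controls return to it during the 16 randomised weeks. The consequence best supported by the text is a bias toward zero in the week 4 and week 16 contrasts in osteocalcin and bone markers. Its size is unknown. It rests on two assumptions: that some controls habitually eat Jarlsberg, and that the markers follow intake within weeks, as section 2.1 reports.

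For BMD, dilution is possible but cannot be quantified from the protocol. The fall in power from 92% to 86, 77 or 66% is an illustrative worst case. This is a cheap improvement, not a defect that invalidates the design.

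**What to change.** Reconcile 1.8.1, 4.1 and 6.2.1 by wording the diet instruction by arm:

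- For controls, keep the protocol's own no-Jarlsberg request in force from screening until the week-16 visit. Repeat it in 6.2.2 and in the patient instructions.
- Apply the cheese-swap clause only to patients who hold study cheese: the Jarlsberg arm from baseline, controls from week 16.
- State that the existing daily form and the MK-9(4H) values at baseline and week 16 will be used to check control-arm adherence. Do not rely on the diet record made after the week-16 visit.

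The cost is a few sentences and a small dietary restriction for some controls over 16 weeks. Habitual eaters in the control arm become a cheese-withdrawal subgroup, which should be acknowledged when the contrast is interpreted, above all for BMD. No new measurement is required.

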#### 6.2.2: Comparative phase

All the participants meet for clinical investigations at week 4 and week 16 in the comparative phase of the study. At week 4, blood samples will be taken for measurements of Osteocalcin and the BTMs. Additionally, concomitant medication, adverse events (AE) and treatment compliance will be recorded. Cheese and vitamin D + Ca for the next 4 weeks will be delivered. A new delivery will be handed over by a representative from the Meddoc team at week 8 and week 12 in the study. The last clinical investigation in this comparative phase will be performed at week 16. The physical examination will be equal with the one performed in the screening phase. The patients must perform a new diet registration during the following 4 days and undergo the second DXA investigation for measurements of BMD. Additionally, the patients will record their change in concomitant medication. Blood samples will be collected for measurements of Osteocalcin, vitamin K2, BTMs, HbA1C, Lipids and other hematological and biochemical variables. Patients with a T-score < -2.5 based on the DXA investigation will be classified as Osteoporotic and withdrawn from the study. If possible and

in accordance with the responsible investigator, the patient will be given Antiresorptive treatment in addition to OED of Jarlsberg cheese and vitamin D + Ca.

The patients randomized to only vitamin D + Ca (Controls) at baseline will now receive OED of Jarlsberg cheese equal with the other patients and continue in the follow-up phase of the study. Cheese for the next 4 weeks will be delivered together with compliance & activity form.

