### 1.6.2 Randomization:

Patients included in the study will be allocated to one of the two treatment groups by block randomization with random block size between 2 and 6.

**1.7: Main variables:** The main response variable will be the change in Bone Mineral Density (BMD) and recorded at baseline and every 16 weeks. The second main variables will be total Osteocalcin (tOC), carboxylated osteocalcin (cOC), the osteocalcin ratio  $R_O$  defined as the ratio between cOC and under-carboxylated osteocalcin (ucOC) [ $R_O = cOC / ucOC$ ] and measured at start, week 4, week 16, week 20, week 32 and week 48. Additionally, the bone markers cross-linked C-telopeptide type I collagen (CTX), procollagen type 1 N-terminal propeptide (PINP), bone specific ALP (BALB) and Parathyroid hormone (PTH) will be measured at the same visits. At baseline and every 16 weeks, the following variables will be measured: Vitamin K2 and the different vitamers MK-7, MK-8, MK-9, and MK-9(4H) used as explanatory variable; Diet registration as controlling variables and HbA1C, Lipids, biochemical variables together with “Quality-of-Life” (QoL) questionnaire as supporting variables. The Interleukins IL-1 $\beta$ , IL6, IL8, IL10 and the Cytokines TNF- $\alpha$ , NF- $\kappa$ B (RANK-L), OPG and TGF- $\beta$  will be measured initially and at the last visit in the study. The Common Terminology Criteria for Adverse Events version 4.0 (CTCAE) will be used for registration of Adverse Events (AE) and toxicity score at every investigation visit.

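### The week-16 diet record is kept in the four days after controls switch to Jarlsberg, and the protocol gives two incompatible times for the baseline record

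*Protocol*

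**What the plan says.** Section 1.7 (Main variables) lists "Diet registration as controlling variables", measured at baseline and every 16 weeks. The flow chart (section 1.11) shows diet registration at screening/baseline and at weeks 16, 32 and 48, and none at weeks 4 or 20.

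**Week 16.** Section 6.2.2 states: "The patients must perform a new diet registration during the following 4 days". Section 5.5 makes this a general rule, with food intake "recorded daily in four consecutive days after inclusion in the screening period and after every 16-week visits". Section 1.8.2 also asks for four days of recording at the main visits but does not say whether they come before or after the visit. On treatment at that visit, section 6.2.2 says: "The patients randomized to only vitamin D + Ca (Controls) at baseline will now receive OED of Jarlsberg cheese equal with the other patients". Section 4.1 also dates the switch at week 16.

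**Baseline.** Section 1.8.1 gives patients the diet app "for registration of the daily food intake during four first consecutively days after baseline". Section 5.5 puts the record in the screening period, and section 6.2.1 puts it in the week between the first clinical investigation and the starting visit. Section 6.2.1 has allocation and the first cheese supply at the baseline visit.

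**Last visits.** Section 6.2.3 repeats the after-the-visit rule for week 32 in the Jarlsberg arm and applies the same procedures to controls through week 48. Section 6.2.4 makes those visits the end of study for the respective arms. Continuing cheese afterwards is an offer (sections 1.8.2 and 6.2.5).

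**The concern.** The intervention is a food, and section 4.1 describes the trial as open. What controls ate during the 16 parallel weeks is therefore a real question. Section 6.2.1 tells participants to keep their usual diet and replace their usual cheese with study cheese, but controls have no study cheese until week 16. The instruction not to eat Jarlsberg appears only for the screening week (section 1.8.1).

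A record started after the switch cannot show whether the arms differed in diet at the end of the comparison. The week-16 vitamin K sample would also be paired with a diet from a different treatment state. This is a matter of data collection: once controls have switched, no analysis plan can recover what they ate before.

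The baseline contradiction matters in a different way. A record begun after Day 0 contains study cheese in one arm only. If it were used for adjustment, it would be affected by treatment and could absorb part of the effect being estimated.

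**Working it through.** The plan states no figure to reproduce on this point. The check sets the recording days against the treatment timeline.

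**Inputs.** Control period of 16 weeks, switch at the week-16 visit (sections 4.1, 6.2.2); four recording days after the visit (sections 5.5, 6.2.2); allocation and first cheese at the baseline visit (section 6.2.1). Assumption: the visit falls on day 112 and cheese is eaten from then on. No section delays the first intake until after the diet record.

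**Week 16.** 16 × 7 = 112, so the control period is days 1–112. The record covers days 113–116. Days under the control regimen: 0 of 4. If the four days ended at the visit: 4 of 4.

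**Each record as written:**

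| Record | Jarlsberg arm | Control arm |
|---|---|---|
| Baseline, section 1.8.1 | 0 of 4 days before allocation; on cheese | 0 of 4 days before allocation; on control regimen |
| Baseline, sections 5.5 and 6.2.1 | 4 of 4 days before allocation | 4 of 4 days before allocation |
| Week 16 | on cheese, as before the visit | on cheese, unlike weeks 0–16 |
| Week 32 | after end of study; cheese optional | on cheese, as before the visit |
| Week 48 | none | after end of study; cheese optional |

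The week-16 fault therefore affects one arm only: the Jarlsberg arm is in the same state before and after the visit, the control arm is not.

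**The two baseline readings:**

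- If sections 5.5 and 6.2.1 govern, the baseline record is a sound pre-randomisation measure. Controls then have no post-randomisation diet record on the control regimen.
- If section 1.8.1 governs, controls do have one such record, at the start of the 16 weeks. The Jarlsberg arm's baseline record then contains the intervention.

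Only one of these can be true.

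**Scale, for illustration.** The nutrition table in section 2.3 gives 770 mg calcium and 27 g protein per 100 g. Section 1.5 gives 57 g and 65 g, but leaves the amounts for the post-menopausal age group as placeholders, so these two are assumed.

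- Calcium: 57 × 7.70 = 439 mg; 65 × 7.70 = 501 mg per day.
- Protein: 57 × 0.27 = 15.4 g; 65 × 0.27 = 17.6 g per day.

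These are gross amounts. Because study cheese is meant to replace usual cheese, the net change is smaller by an amount the protocol does not give. The timing fault does not depend on the dose.

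**The case against.** The strongest reply is that little depends on this record. Diet is not an endpoint, and section 11.2 specifies ANCOVA with a baseline observation as covariate without naming diet. That is right, and it makes any harm from over-adjustment conditional on a use the protocol does not state.

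Second, Jarlsberg intake is captured elsewhere: all patients fill in a daily form for Jarlsberg and supplements (section 6.2.1), and MK-9(4H), in which Jarlsberg is rich (section 2.3), is measured at baseline and every 16 weeks (section 5.3). This stands for Jarlsberg itself. It does not cover other cheese, total calcium or the rest of the diet.

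Third, the week-16 record covers all food, and patients are told to change only their cheese, so its non-cheese part is still partly informative. This also stands. The flow chart labels the visit as time zero of the switch phase as well, but a record begun after the switch is no pre-switch baseline either.

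A reader might infer more: that diet registration is useless as a control, or that controls lack any control-period record and the baseline covariate is contaminated as well. The documents do not support this. The screening-week version is a valid baseline measure, and the two harms need opposite readings of the baseline timing. Nor does any section say the week-16 record will be treated as control-phase intake.

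**Conclusion.** The timing fault holds. As written, none of the four week-16 recording days describes control-arm diet during the randomised comparison, provided cheese starts at the visit as section 6.2.2 implies. The baseline timing is a plain contradiction between section 1.8.1 and sections 5.5 and 6.2.1, with one of two alternative harms depending on which governs.

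The consequence is limited: a supporting variable is measured in the wrong treatment state in one arm. No stated analysis or sample size rests on it, and no bias in the BMD comparison has been shown. The records after the last visits are a lesser matter, outside the randomised comparison. The change is still worth making because the information cannot be recovered later and costs almost nothing to collect correctly.

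**What to change.** 1. Baseline: amend section 1.8.1 to agree with sections 5.5 and 6.2.1, with a four-day record in the screening week, completed before allocation.
2. Later records: amend sections 1.8.2, 5.5, 6.2.2 and 6.2.3 so that the week-16, 32 and 48 records cover the four days ending at the visit, before any switch or end of treatment.
3. State the use: the week-16 record remains post-randomisation even when moved, so use it to describe diet by arm and not as an adjustment covariate for the treatment contrast. Any adjustment for diet should use the pre-allocation record.

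The number of records and the app stay the same. The cost is the amendment text and a reminder to patients ahead of each main visit.
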